5.3.6 Study Discontinuation

The following will be performed at the time of study discontinuation, whether due to study completion or early withdrawal from study participation

- Physical Exam and evaluation of ECOG PS
- Vital signs (Blood pressure, heart rate, temperature, weight)
- CBC with differential and platelets
- Serum chemistry panel including sodium, potassium, chloride, CO₂, calcium, serum creatinine, BUN, total bilirubin, alkaline phosphatase, AST, ALT and TSH
- Assessment of adverse events and concomitant medications

5.3.7 Safety Assessment (to be performed 28 Days (+/- 7 days) after study discontinuation)

- Assessment of adverse events and concomitant medications

5.3.8 Follow-Up (to be performed every 3 months for the first 3 years after study discontinuation, and then yearly thereafter)

- Review of anti-cancer treatments
- Review of progression and survival information

Assessments to be performed at screening and during scheduled study visits are also outlined in Section 2 Table of Study Assessments.

At treatment discontinuation, subjects will undergo off study evaluations per the Schedule of Assessments, Section 2. In addition, a safety assessment will be done approximately 28 days after the last dose of protocol therapy. Follow-up contact with the subjects should occur at a minimum of 3 months during the first 3 years after finishing maintenance phase and annually after that.

5.4 Drug Administration

5.4.1 Dosing Regimen

Lenalidomide capsule will be given by mouth daily (on days 1-28 of each 28 day cycle). Lenalidomide starting dose will be determined as detailed below.

[figure not shown]
First 3 enrolled patients: The starting dose of lenalidomide for the first 3 subjects enrolled will be 10 mg daily. Three subjects must complete a full 28-day cycle before further study enrollment can proceed. The next cohort of 3 patients must also complete a full 28 day cycle before further enrollment can proceed. The lenalidomide starting dose for the remaining subjects will depend on the observance of dose limiting toxicities in this first cohort of 6 patients.

No DLTs observed: If the first 3 patients complete the first full cycle of study treatment without experiencing a DLT, then 3 additional patients will be enrolled. If 0 or 1 of 6 patients experience DLT, then 10 mg will be considered the appropriate dose and the remainder of enrolled subjects will also use a lenalidomide starting dose of 10 mg daily (on days 1-28 of each 28 day cycle). If 2 patients from the second 3-person cohort experience a DLT during the first cycle of study treatment, then 3 patients will be treated with lenalidomide at a dose of 5 mg daily (days 1-28 of each 28 day cycle). 3+3 assessment will be conducted at 5 mg.

One DLT observed: If 1 out of the first 3 patients experiences a dose limiting toxicity during the first cycle of study treatment, an additional 3 patients will be treated with a starting dose of 10 mg daily and must complete a full cycle of study treatment before study enrollment can resume. If no additional patients experience a DLT after the first cycle of treatment, then 10 mg will be considered the appropriate dose and the remainder of study patients will begin treatment using a lenalidomide dose of 10 mg daily. If 1 patient in the second 3-person cohort experiences a DLT, then 3 patients will be treated with lenalidomide at a dose of 5 mg by mouth daily. The 3+3 assessment will be conducted at 5 mg.

Two DLT's: If 2 patients from the first 3-person cohort experience a DLT during the first cycle of study treatment, then 3 patients will be treated with lenalidomide at a dose of 5 mg daily (days 1-28 of each 28 day cycle). 3+3 assessment will be conducted at 5 mg.

Two DLT's at 5 mg dose level: If the starting dose level is determined to be 5 mg daily and 2 or more patients experience DLT's at this dose level, the study will be stopped.

Dosing will be at approximately the same time each day. Prescriptions must be filled within 7 days.

See section 5.6.1.2 for concomitant anti-coagulation.

If a dose of lenalidomide is missed, it should be taken as soon as possible on the same day. If it is missed for the entire day, it should not be made up.

Patients who take more than the prescribed dose of lenalidomide should be instructed to seek emergency medical care if needed and contact study staff immediately.

Subjects experiencing adverse events may need study treatment modifications (See section 5.5).

5.4.2 Special Handling Instructions

Females of childbearing potential should not handle or administer lenalidomide unless they are wearing gloves.

5.4.3 Record of Administration

Accurate records will be kept in the source documents of all drug administration (including prescribing and dosing). Subjects should also record lenalidomide dosing on the study calendar during each cycle.

5.5 Dose Continuation, Modification and Interruption

Subjects will be evaluated for AEs at each visit using the NCI CTCAE v4.0 as a guide for the grading of severity. Sections below describe dose reduction steps, instructions for initiation of a new cycle of therapy and dose modifications during a cycle of therapy.

5.5.1 Dose Reduction Steps

Table 1: Lenalidomide Dose Modification Steps	
Current Lenalidomide Dose	One Level Dose Reduction
10 mg daily (on days 1-28 of each 28 day cycle)	5 mg daily (on days 1-28 of each 28 day cycle)*
5 mg daily (on days 1-28 of each 28 day cycle)*	See * below

* Lenalidomide 5 mg daily (on days 1-28 of each 28 day cycle) is the minimum lenalidomide dose. Lenalidomide will be discontinued in patients who cannot tolerate this dose. However, patients who experience toxicity requiring dose reduction while receiving lenalidomide 5 mg daily may, at the discretion of their physician, have their dose held until toxicity resolves as described in Sections 5.5.2 and 5.5.3, and then restart lenalidomide 5 mg daily. If the same toxicity recurs at lenalidomide 5 mg daily, consideration should be given to discontinuing lenalidomide.

5.5.2 Instructions for Initiation of a New Cycle

A new course of treatment may begin on the scheduled day 1 of a new cycle if:

- The ANC is $\geq 1,000/\mu\text{L}$
- The platelet count is $\geq 50,000/\mu\text{L}$
- Any drug-related rash or neuropathy that may have occurred has resolved to \leq grade 1 severity.
- Any other drug-related adverse events that may have occurred have resolved to \leq grade 2 severity.

If these conditions are not met on day 1 of a new cycle, the subject will be evaluated weekly and a new cycle of treatment will not be initiated until the toxicity has resolved as described above.

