The metabolic profile of lenalidomide in humans has not been studied. In healthy volunteers, approximately two-thirds of lenalidomide is eliminated unchanged through urinary excretion. The process exceeds the glomerular filtration rate and therefore is partially or entirely active. Half-life of elimination is approximately 3 hours.

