5.3.4 Cycles 2-24, Day 1 (+/- 7 days)

- Physical Examination and evaluation of ECOG PS
- Vital signs: blood pressure, heart rate, temperature and weight
- CBC with differential and platelets
- Serum Chemistry panel including sodium, potassium, chloride, CO₂, calcium, serum creatinine, BUN, total bilirubin, alkaline phosphatase, AST, ALT
- Serum pregnancy test (for women of child-bearing potential)
- Review of interim adverse events and concomitant medications

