5.5.3 Instructions for Dose Modifications or Interruption During a Cycle

Dose delay and dose reduction rules are as follows and in the table below.

- Lenalidomide dose reduction steps are outlined in Section 5.5.1.
- For treatment interruptions during a cycle, the 28-day schedule of each cycle will continue to be followed. Missed doses of lenalidomide are not made up.
- For treatment interruptions that delay the scheduled start of a new cycle, when toxicity has resolved as required to allow the start of a new cycle (Section 5.5.2), the restart day of therapy becomes day 1 of the next cycle.

Table 2: Dose Modifications :	
NCI CTC Toxicity Grade	Dose Modification Instructions (also see Instructions for Initiation of a New Cycle above)
Grade 3 neutropenia associated with fever (T ≥ 38.5° C) or Grade 4 neutropenia	
 • Hold (interrupt) lenalidomide dose. • Follow CBC weekly. • If neutropenia has resolved to ≤ grade 2 prior to Day 28 of the current cycle, restart lenalidomide at next lower dose level and continue through the scheduled Day 28 of the current cycle. Otherwise, omit for remainder of cycle and reduce the dose of lenalidomide by 1 dose level at the start of the next cycle. Omitted doses are not made up. If neutropenia is the only toxicity for which a dose reduction is required, G-CSF may be used and the lenalidomide dose maintained.
Thrombocytopenia ≥Grade 3 (platelet count < 50,000/mm³)	
 • Hold (interrupt) lenalidomide dose. • Follow CBC weekly. • If thrombocytopenia resolves to ≤ grade 2 prior to Day 28 of the current cycle, restart lenalidomide at next lower dose level and continue through the scheduled Day 28 of the current cycle. Otherwise, omit for remainder of cycle and reduce the dose of lenalidomide by 1 dose level at the start of the next cycle. Omitted doses are not made up. • Hold prophylactic anti-coagulation, if applicable. • Restart prophylactic anti-coagulation when platelet count is ≥ 50,000/mm³.
Non-blistering rash	
 • If Grade 3, hold (interrupt) lenalidomide dose. Follow weekly. • If the toxicity resolves to ≤ grade 1 prior to Day 28 of the current cycle, restart lenalidomide at next lower dose level and continue through the scheduled Day 28 of the current cycle. Otherwise, omit for remainder of cycle and reduce the dose of lenalidomide by 1 dose level at the start of the next cycle. Omitted doses are not made up.
Grade 3	

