Grade 4	
 • If Grade 4, discontinue lenalidomide. Remove patient from study.
Desquamating (blistering) rash- any Grade	
 • Discontinue lenalidomide. Remove patient from study.
Lenalidomide-related neuropathy	
 • If Grade 3, hold (interrupt) lenalidomide dose. Follow at least weekly. • If the toxicity resolves to ≤ grade 1 prior to Day 28 of the current cycle, restart lenalidomide at next lower dose level and continue through the scheduled Day 28 of the current cycle. Otherwise, omit for remainder of cycle and reduce the dose of lenalidomide by 1 dose level at the start of the next cycle. Omitted doses are not made up.
Grade 3	
Grade 4	
 • If Grade 4, discontinue lenalidomide. Remove patient from study.
Venous thrombosis/embolism ≥ Grade 3	
 • Hold (interrupt) lenalidomide and start therapeutic anticoagulation, if appropriate. • Restart lenalidomide at investigator's discretion (maintain dose level). • See Anticoagulation Consideration (Section 5.6.1.2)
Hyperthyroidism or hypothyroidism	
 • Omit lenalidomide for remainder of cycle, evaluate etiology, and initiate appropriate therapy. • See Instructions for Initiation of a New Cycle and reduce the dose of lenalidomide by 1 dose level.

Table 2: Dose Modifications :	
NCI CTC Toxicity Grade	Dose Modification Instructions (also see Instructions for Initiation of a New Cycle above)
Creatinine \geq Grade 2 ($>1.5 - 3.0 \times$ baseline)	
 • Hold lenalidomide dose until resolved to grade < 2. When re-starting, reduce lenalidomide by 1 dose level. Omitted doses are not made up.
Other non-hematologic toxicity \geq Grade 3	
 • Hold (interrupt) lenalidomide dose. Follow at least weekly. • If the toxicity resolves to \leq grade 2 prior to Day 28 of the current cycle, restart lenalidomide and continue through the scheduled Day 28 of the current cycle. Otherwise, omit for remainder of cycle. Omitted doses are not made up. For toxicity attributed to lenalidomide, reduce the lenalidomide dose by 1 dose level when restarting lenalidomide.

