6.2 Adverse Event Reporting

The adverse event recording and reporting period will begin with each subject’s first dose of lenalidomide and will end twenty-eight days after each patient’s last dose of lenalidomide, or upon resolution of any treatment-related adverse events, should their duration extend beyond the 28-day reporting period. Pre-existing conditions (those events existing prior to each patient’s first dose of lenalidomide) will not be reported as adverse events unless they worsen in grade or severity.

Toxicity will be scored using CTCAE Version 4.0 for toxicity and adverse event reporting. A copy of the CTCAE Version 4.0 can be downloaded from the CTEP homepage ([HTTP://CTEP.INFO.NIH.GOV](http://CTEP.INFO.NIH.GOV)). All appropriate treatment areas should have access to a copy of the CTCAE Version 4.0. All adverse clinical experiences, whether observed by the investigator or reported by the patient, must be recorded, with details about the duration and intensity of each episode, the action taken with respect to the test drug, and the patient’s outcome. The investigator must evaluate each adverse experience for its relationship to the test drug and for its seriousness.

The investigator must appraise all abnormal laboratory results for their clinical significance. If any abnormal laboratory result is considered clinically significant, the investigator must provide details about the action taken with respect to the test drug and about the patient's outcome on the adverse event CRF. Lab abnormalities graded \leq grade 2 in severity will not be reported as adverse events, unless deemed to be clinically significant by the treating physician.

Lymphopenia of any grade will not be considered an adverse event.

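### For a drug-related grade 2 creatinine rise on day 1, Section 5.5.2 allows the new cycle to start while the Table 2 creatinine row requires a hold and a dose reduction, and no precedence is stated

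*Combined protocol and SAP*

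**What the plan says.** Section 5.5.2 opens with "A new course of treatment may begin on the scheduled day 1 of a new cycle if" and then gives four conditions: an ANC limit, a platelet limit, rash or neuropathy at grade 1 or less, and "Any other drug-related adverse events that may have occurred have resolved to" grade 2 or less. Creatinine is not named. If a condition fails, the patient is evaluated weekly until it is met.

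Table 2 has a separate row for creatinine of grade 2 or higher, given as more than 1.5 to 3.0 times baseline. Its instruction is "Hold lenalidomide dose until resolved to grade < 2. When re-starting, reduce lenalidomide by 1 dose level". The row does not ask whether the rise is drug-related.

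Table 2 sits in Section 5.5.3, "Instructions for Dose Modifications or Interruption During a Cycle", and its header adds "also see Instructions for Initiation of a New Cycle above". A bullet in 5.5.3 says that when an interruption delays a cycle, treatment restarts once toxicity has resolved as 5.5.2 requires. The footnote to Table 1 in 5.5.1, on holding and restarting at 5 mg, refers to both 5.5.2 and 5.5.3 for what counts as resolved.

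Section 5.3.4 schedules a "Serum Chemistry panel including sodium, potassium, chloride" and further items, creatinine among them, on day 1 of cycles 2-24. The Section 2 schedule agrees.

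**The concern.** The same laboratory value, at the visit where the decision to start a cycle is made, meets two instructions that cannot both settle the dose. Under 5.5.2 a drug-related grade 2 rise is acceptable and carries no reduction. Under Table 2 the drug is stopped, the value must fall below grade 2, and the dose comes down one level.

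The choice has consequences in both directions. One route continues an unchanged dose of a drug of which, by Section 5.1.1.3, "approximately two-thirds of lenalidomide is eliminated unchanged through urinary excretion" (in healthy volunteers). The other interrupts treatment, and under Section 5.7 an interruption of 28 or more consecutive days ends study treatment. Section 8.2 lists dose adjustments not completed per protocol among its examples of submittable exceptions and deviations, so a start that complies with 5.5.2 could be classed as a deviation from Table 2.

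**Working it through.** No sample size, power or error rate is involved. The check sets the two rules side by side and compares them with the visit schedule.

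**1. Outcome on day 1 under each rule**

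| Creatinine on day 1 | Section 5.5.2 | Table 2 creatinine row | Result |
|---|---|---|---|
| Grade 1 | Start allowed | No action | Agree |
| Grade 2, drug-related adverse event | Start allowed, no reduction | Hold until below grade 2, then one level lower | Conflict |
| Grade 3 or higher, drug-related adverse event | No start until grade 2 or less | Hold until below grade 2, then one level lower | Both stop the start; release point differs |
| Grade 2 or higher, not drug-related or not counted as an adverse event | No condition applies | Hold, then one level lower | 5.5.2 is silent; only Table 2 speaks |

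The direct contradiction is in the second row, with a related disagreement on the release point in the third.

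**2. Does the text say which rule wins?** The Table 2 header only cross-refers to 5.5.2. The 5.5.3 restart bullet makes 5.5.2 the test for restarting after a delayed cycle. For a drug-related creatinine rise, that test is met at grade 2, where the Table 2 hold still applies. The 5.5.1 footnote cites both sections. None of these sets an order.

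**3. Do other toxicities show the same mismatch?**
- Rash and neuropathy: release at grade 1 or less in both sections.
- Platelets: 50,000 in 5.5.2; Table 2 defines grade 3 or higher as below 50,000 and releases at grade 2 or less, which is the same point.
- Other non-hematologic toxicity: grade 2 or less in both.
- Thyroid: the row refers to the new-cycle instructions by name.
- Creatinine: grade 2 or less through the general line of 5.5.2, below grade 2 in Table 2.

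Among these, creatinine is the row whose release limit does not match, which suggests an omission from 5.5.2 and not a deliberate second rule.

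**4. When would it arise?** On-treatment chemistry after cycle 1 is scheduled on day 1 of cycles 2-24: 24 − 2 + 1 = 23 visits for a patient who completes treatment. Section 5.3.6 adds a panel at discontinuation, but no cycle starts there. Unscheduled visits, and weekly evaluation after a failed start, can add values. The 23 visits are opportunities; the documents give no expected rate of grade 2 creatinine.

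**5. Does it reach the trial's decision rules?** Section 10.3 limits non-hematologic DLTs to grade 3 or higher in the first 28 days. A grade 2 rise is below that threshold at any time, and day 1 of cycle 2 nominally follows the window. The 3+3 rules (10.4) and the phase II termination table (10.5) count only DLTs. The PFS12 definition (10.3) and its success threshold (10.6) do not refer to dose.

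**The case against.** The best defence is that the two texts can be read together. Section 5.5.2 is permissive, Table 2 is directive, and a physician who holds the drug breaches neither. The creatinine row is specific and, unlike the blood count, rash and neuropathy rows, is not tied to day 28 of the current cycle, so it can be taken to run across the cycle boundary. A cycle started with grade 2 creatinine would meet the hold condition at once. That is a sensible reading, but the reader has to supply it. The protocol places Table 2 under mid-cycle changes, and its restart bullet points to 5.5.2, so the release threshold after a delayed start stays unsettled.

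Other parts of the defence stand and limit the point:

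- For a rise that is not drug-related, or that Section 6.2 keeps from being an adverse event, 5.5.2 says nothing. A reader might infer that the difference in attribution widens the contradiction; in that case Table 2 is the only text that speaks.
- A reader might infer a recording gap, because laboratory changes up to "grade 2 in severity will not be reported as adverse events, unless deemed to be clinically significant by the treating physician". Section 6.2 also requires the action taken with the drug to be entered on the adverse event form for clinically significant results, and 5.4.3 requires accurate dosing records. Asking for more is a preference, not a correction.
- A reader might infer that different sites would diverge. The synopsis describes a single-institution study, so any variation is between physicians or between visits.

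**Conclusion.** The point holds as a contradiction in the current text. It is confined to drug-related creatinine: whether a cycle may start at grade 2, at what grade dosing resumes after a delay, and whether the dose is reduced. It can arise at up to 23 scheduled visits per patient, with frequency unknown. It bears on patient safety and on consistent dosing after cycle 1.

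Two stronger readings are not supported. The first is that the primary safety conclusion is weakened. The primary endpoint is DLT, and neither DLT counts, the 3+3 decisions, the phase II stopping rule nor PFS12 changes with the rule chosen. The second is that the two-thirds urinary figure lets one calculate how far exposure would rise at a given creatinine. That requires renal clearance to fall in inverse proportion to creatinine. Section 5.1.1.3 says renal elimination exceeds glomerular filtration and is at least partly active, and the figure comes from healthy volunteers, so the documents do not support the calculation.

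The conclusion assumes that creatinine belongs under the general line of 5.5.2, since no other line covers it. It takes no view on which threshold is clinically right.

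**What to change.** Reconcile Section 5.5.2 and the 5.5.3 restart bullet with the Table 2 creatinine row, so that a single creatinine criterion governs both the start of a cycle and dosing within it. State whether that criterion applies to any rise or only to a drug-related one. The sponsor-investigator decides the criterion.

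The cost is a sentence or two in a protocol amendment. It needs no new tests, visits or data fields, and no change to the statistical section.

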5.5.3 Instructions for Dose Modifications or Interruption During a Cycle

Dose delay and dose reduction rules are as follows and in the table below.

- Lenalidomide dose reduction steps are outlined in Section 5.5.1.
- For treatment interruptions during a cycle, the 28-day schedule of each cycle will continue to be followed. Missed doses of lenalidomide are not made up.
- For treatment interruptions that delay the scheduled start of a new cycle, when toxicity has resolved as required to allow the start of a new cycle (Section 5.5.2), the restart day of therapy becomes day 1 of the next cycle.

Table 2: Dose Modifications :	
NCI CTC Toxicity Grade	Dose Modification Instructions (also see Instructions for Initiation of a New Cycle above)
Grade 3 neutropenia associated with fever (T ≥ 38.5° C) or Grade 4 neutropenia	
 • Hold (interrupt) lenalidomide dose. • Follow CBC weekly. • If neutropenia has resolved to ≤ grade 2 prior to Day 28 of the current cycle, restart lenalidomide at next lower dose level and continue through the scheduled Day 28 of the current cycle. Otherwise, omit for remainder of cycle and reduce the dose of lenalidomide by 1 dose level at the start of the next cycle. Omitted doses are not made up. If neutropenia is the only toxicity for which a dose reduction is required, G-CSF may be used and the lenalidomide dose maintained.
Thrombocytopenia ≥Grade 3 (platelet count < 50,000/mm³)	
 • Hold (interrupt) lenalidomide dose. • Follow CBC weekly. • If thrombocytopenia resolves to ≤ grade 2 prior to Day 28 of the current cycle, restart lenalidomide at next lower dose level and continue through the scheduled Day 28 of the current cycle. Otherwise, omit for remainder of cycle and reduce the dose of lenalidomide by 1 dose level at the start of the next cycle. Omitted doses are not made up. • Hold prophylactic anti-coagulation, if applicable. • Restart prophylactic anti-coagulation when platelet count is ≥ 50,000/mm³.
Non-blistering rash	
 • If Grade 3, hold (interrupt) lenalidomide dose. Follow weekly. • If the toxicity resolves to ≤ grade 1 prior to Day 28 of the current cycle, restart lenalidomide at next lower dose level and continue through the scheduled Day 28 of the current cycle. Otherwise, omit for remainder of cycle and reduce the dose of lenalidomide by 1 dose level at the start of the next cycle. Omitted doses are not made up.
Grade 3	
Grade 4	
 • If Grade 4, discontinue lenalidomide. Remove patient from study.
Desquamating (blistering) rash- any Grade	
 • Discontinue lenalidomide. Remove patient from study.
Lenalidomide-related neuropathy	
 • If Grade 3, hold (interrupt) lenalidomide dose. Follow at least weekly. • If the toxicity resolves to ≤ grade 1 prior to Day 28 of the current cycle, restart lenalidomide at next lower dose level and continue through the scheduled Day 28 of the current cycle. Otherwise, omit for remainder of cycle and reduce the dose of lenalidomide by 1 dose level at the start of the next cycle. Omitted doses are not made up.
Grade 3	
Grade 4	
 • If Grade 4, discontinue lenalidomide. Remove patient from study.
Venous thrombosis/embolism ≥ Grade 3	
 • Hold (interrupt) lenalidomide and start therapeutic anticoagulation, if appropriate. • Restart lenalidomide at investigator's discretion (maintain dose level). • See Anticoagulation Consideration (Section 5.6.1.2)
Hyperthyroidism or hypothyroidism	
 • Omit lenalidomide for remainder of cycle, evaluate etiology, and initiate appropriate therapy. • See Instructions for Initiation of a New Cycle and reduce the dose of lenalidomide by 1 dose level.

Table 2: Dose Modifications :	
NCI CTC Toxicity Grade	Dose Modification Instructions (also see Instructions for Initiation of a New Cycle above)
Creatinine \geq Grade 2 ($>1.5 - 3.0 \times$ baseline)	
 • Hold lenalidomide dose until resolved to grade < 2. When re-starting, reduce lenalidomide by 1 dose level. Omitted doses are not made up.
Other non-hematologic toxicity \geq Grade 3	
 • Hold (interrupt) lenalidomide dose. Follow at least weekly. • If the toxicity resolves to \leq grade 2 prior to Day 28 of the current cycle, restart lenalidomide and continue through the scheduled Day 28 of the current cycle. Otherwise, omit for remainder of cycle. Omitted doses are not made up. For toxicity attributed to lenalidomide, reduce the lenalidomide dose by 1 dose level when restarting lenalidomide.

